#### Summary tables will be prepared for:

- All TEAEs
- All non-serious TEAEs
- TEAEs by causality (related/unrelated)
- TEAEs by severity
- TEAEs leading to death
- TEAEs leading to withdrawal of study drug
- Treatment emergent SAEs

#### Data listings will be provided for:

- All AEs sorted by centre and subject number
- All AEs sorted by MedDRA SOC and PT
- SAEs
- AEs leading to death
- AEs leading to withdrawal of study drug
- Pre-treatment AEs

#### 4.3.2 Other safety endpoints

#### 4.3.2.1 Laboratory measurements

Absolute values and change from baseline in hematology and clinical biochemistry parameters will be summarized by visit and treatment group using descriptive statistics.

Frequency and percentage for categorical urinalysis data will be presented by visit and treatment group, when relevant.

Laboratory values will be flagged if outside the reference range.

A listing of abnormal values will be presented.

#### 4.3.2.2 Vital signs and ECG

Descriptive statistics for vital signs parameters (systolic and diastolic blood pressure, heart rate, and body temperature), weight and 12-lead ECG parameters along with ECG interpretation will be presented in the same way as the laboratory parameters.

#### 4.3.2.3 Skin tolerability assessment

Frequency and percentage for categorical skin tolerability assessment data will be presented by visit and treatment group.

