#### 1.1.2 Endpoints

The primary endpoint of this study (double-blind treatment groups only) is:

• The change from baseline in WOMAC pain sub-score (questions 1 to 5) in the target knee as evaluated at week 4.

The secondary endpoints of this study (double-blind treatment groups only) are:

- Changes from baseline in WOMAC total score and the WOMAC function and stiffness scores at week 4
- Changes from baseline in constant and intermittent OA pain assessed by ICOAP scores at week 4
- Changes from baseline in WOMAC pain weight-bearing score (questions 1, 2, and 5) and non-weight bearing score (questions 3 and 4) at week 4
- Changes from baseline in physical function assessed by the chair-stand test at week 4
- OMERACT-OARSI responder rate at week 4
- Total dose of rescue medication calculated as the sum of tablets used, based on pill counts
- Time between baseline and first use of rescue medication
- Changes from baseline in WOMAC pain sub-score (questions 1 to 5) between groups receiving AMZ001 QD and BID in the target knee as evaluated at week 4

- Changes from baseline in constant and intermittent OA pain assessed by ICOAP scores between groups receiving AMZ001 QD and BID at week 4
- Changes from baseline in WOMAC pain weight-bearing score (questions 1, 2, and 5) and non-weight bearing score (questions 3 and 4) between groups receiving AMZ001 QD and BID at week 4
- Changes from baseline in physical function assessed by the chair-stand test between AMZ001 QD and BID at week 4
- Changes from baseline in WOMAC total score and the WOMAC function and stiffness scores between AMZ001 QD and BID at week 4.
- Changes from baseline in the impact of OA on daily living as assessed by the PGA score at week 4
- Changes from baseline in work productivity and activity assessed by the WPAI at week 4
- Changes from baseline in quality of life assessed by the EQ5D at week 4

The safety endpoints of this study are:

- Nature, incidence and severity of AEs
- Changes in laboratory safety parameters, vital signs, 12-lead ECG parameters and weight
- Nature, incidence and severity of skin reactions on the application site

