- 1. If subject is washed out of analgesics at Screening Visit 1a, the examinations scheduled for screening visits 1a and 1b can be performed on the same day.
- 2. Phone call.
- 3. Skin assessment to be performed prior to application of study drug at baseline visit.
- 4. Subjects will be educated on appropriate expectations around their participation in a clinical study and the importance of reliably consistently and accurately reporting their pain throughout the study.
- 5. WOMAC pain sub-score (5 questions) to be assessed on a daily basis on paper at home during first week of treatment, i.e. the period between Visit 2 and Visit 3.
- 6. Assessed without analgesic medication for five half-lives of the analgesic.
- 7. WOMAC assessment of hips should only be performed at the screening visit.

- 8. To be completed daily in the evening during the first week of treatment, i.e. between Visit 2 and Visit 3). In the period between other subsequent visits, the questionnaire will be completed during the evening of the day prior to the next visit.
- 9. Only weight collected.
- 10. Conditions previously unknown to the subject at the time of the screening visit will be recorded as medical history. All subsequent events will be recorded as adverse events.
- 11. To be collected/dispensed if previously dispensed supply of rescue medication was depleted and empty packaging returned to site.
- 12. Collection of remaining rescue medication at Visit 6. Empty packaging of previously dispensed kit should be returned to the site if new rescue medication is requested.
- 13. Serum test at screening visit, urine dipstick at all other visits.
- 14. To be done after IMP application and questionnaire/test completion (approximately 1-2 hours after IMP application). Exact time of IMP application and time of blood sampling must be documented.
- 15. Dispensation is not mandatory for subjects allocated to Voltaren® gel

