### 3.4 Safety analysis set

The SAF will include all subjects who have taken at least one application of trial treatment. Subjects will be analysed according to the actual treatment they receive.

The actual treatment received by each subject will be established by the unblinded data-manager. At the Blind Data Review Meeting, the unblinded data-manager will present a **subject blinded** list of treatment misallocations for review. For subjects misallocated treatment, the actual treatment received will be decided based on below categories and documented. For subjects receiving treatment as per the randomization, actual treatment is identical to planned treatment.

Since dispensation of IMP occurs at multiple timepoints (Visit 2, Visit 4 and as needed), subjects will fall into one of the following three actual treatment categories:

- 1. IMP is dispensed correctly on all occasions.
- 2. IMP is consistently dispensed incorrectly on all occasions i.e. the subject received the same (incorrect) treatment throughout the study and the IMP received corresponds to one of the study treatment groups.
- 3. IMP is dispensed incorrectly on one or more occasions and the subject did not consistently receive IMP corresponding to one of the study treatment groups.

In order not to bias the safety reporting of the study treatment groups, any subjects falling into category 3 above will be included in the SAF under a separate treatment group 'AMZ – misallocations' and will therefore not be included in the safety summaries for any of the study treatment groups.

The SAF will be used for all safety and tolerability summaries.

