### 4.1.1 Data presentation

All statistical tests will be performed using a two-sided test at a 5% significance level. Results from analyses will be presented with estimates, 95% confidence intervals (CIs) and p-values.

Numerical data will be presented in summary tables by number of observations (n), the number of missing values (missing), arithmetic mean, standard deviation (SD), median, first and third quartiles (Q1, Q3), minimum (min) and maximum (max) values. The mean, median, Q1 and Q3 will be reported to one decimal place more than the raw data, the standard deviation to two decimal places more than the raw data and the minimum and maximum values to the same precision as the raw data. The summary statistics presented for categorical data will be the

number of observations (n), the number of missing values (missing) and the count and percentage of subjects in each category. Number of events will also be reported where applicable.

All data will be listed by treatment group, subject and time point (if applicable). Age and sex will be displayed in all listings.

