#### 4.3.1 Adverse events

Adverse events (AEs) will be classified according to MedDRA version 21.0.

An AE overview summary table will be prepared including the number of subjects reporting an AE, the percentage of subjects (%) with an AE, and the number of events (E) reported for the following categories:

- Treatment-emergent AEs
- Deaths
- Serious adverse events (SAEs)
- AEs leading to withdrawal of study drug
- Severe and life-threatening AEs
- Adverse drug reactions

Treatment emergent AEs are defined as any AE that has occurred after the first administration of IMP administration.

ADRs are defined as all untoward and unintended responses to an IMP related to any dose administered, i.e. all AEs which are probably or possibly related to IMP.

Treatment-emergent AEs will be summarized in a table by dictionary level, i.e., system organ class (SOC) and preferred term (PT) for MedDRA. The table will display the total number of subjects reporting an AE, the percentage of subjects (%) with an AE and the number of events (E)

reported. AEs will be presented by SOC sorted alphabetically and PT sorted in decreasing frequency of occurrence.

Pre-treatment AEs will be listed only.

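### The skin-reaction safety endpoint asks for incidence and severity, but the scheduled skin assessment is summarised only by visit, so no table gives subjects ever affected or their worst grade

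*SAP*

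**What the plan says.** SAP 1.1.2 lists three safety endpoints: adverse events; changes in laboratory values, vital signs, ECG and weight; and, as an item of its own, "Nature, incidence and severity of skin reactions on the application site".

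The schedule (Protocol Table 2, SAP Table 1) places a skin tolerability assessment at V2, V3, V4, V5 and V6. The V2 assessment comes before treatment: "Skin assessment to be performed prior to application of study drug at baseline visit". There are therefore one pre-application and four post-baseline assessments.

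The analysis of these data is the single sentence of SAP 4.3.2.3: "Frequency and percentage for categorical skin tolerability assessment data will be presented by visit and treatment group".

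SAP 4.1.1 says that categorical summaries show "number of observations (n), the number of missing values (missing) and the count and percentage of subjects in each category". It does not say whether the percentage is taken over subjects observed at the visit or over all subjects in the set.

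SAP 3.4 defines the safety set: "The SAF will include all subjects who have taken at least one application of trial treatment". Subjects are analysed by the treatment actually received.

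SAP 4.3.1 separately plans treatment-emergent AE tables by system organ class and preferred term, with subject counts and percentages. It also plans tables of "TEAEs by severity" and "TEAEs leading to withdrawal of study drug".

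**The concern.** Incidence is a property of subjects over the treatment period: did this person have a reaction at any time, and how bad was it at worst? A by-visit table answers a different question, namely what share of those assessed at a given visit had a finding then. A subject whose reaction appears at V3 and clears by V4, and another who first reacts at V5, appear in different columns that cannot be added without knowing who they are. SAP 4.3.2.3 also makes no use of the V2 assessment to separate new or worse findings from those already present.

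Safety and tolerability is a secondary objective, and SAP 2.2 says that the trial will inform on the tolerability of twice-daily against once-daily use. For a gel applied to the skin, that comparison is most naturally made on the proportion of subjects with a new local reaction and its worst grade in each arm. No planned table derives either from the assessment designed to measure it.

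**Working it through.** The documents give no skin-reaction rate, so there is no figure of the plan's own to reproduce. The rates below are assumptions that show how far the two summaries can differ.

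**Inputs from the documents.** Four post-baseline assessments (schedule); 120 subjects per double-blind arm (SAP 2.2).

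**Step 1: what a by-visit table leaves open.** Assume complete data and 5% affected at each visit, that is 0.05 × 120 = 6 subjects.

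- Same six subjects each time: ever affected = 6/120 = 5%.
- Different subjects each time: 4 × 6 = 24, and 24/120 = 20%.
- Visits independent: 1 − 0.95^4 = 0.185, or 18.5%, about 22 of 120.

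The planned table is identical in all three cases.

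**Step 2: a simple course of reactions.** Let h be the chance of a first reaction in each interval among those not yet affected, r the share resolved by the next visit, and w the share of affected subjects who withdraw after the visit that records the reaction. There is no recurrence, and other subjects stay in. Then:

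- affected at visit v: A_v = h(1 − h)^(v−1) + (1 − w)(1 − r)A_(v−1)
- withdrawn by visit v: W_v = W_(v−1) + wA_(v−1)
- percentage on observed n: A_v / (1 − W_v)
- ever affected: 1 − (1 − h)^4

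| h | Resolved by next visit | Affected who withdraw | V3 % | V4 % | V5 % | V6 % | Ever affected % |
|---|---|---|---|---|---|---|---|
| 2% | all | none | 2.0 | 2.0 | 1.9 | 1.9 | 7.8 |
| 2% | half | none | 2.0 | 3.0 | 3.4 | 3.6 | 7.8 |
| 2% | either | all | 2.0 | 2.0 | 2.0 | 2.0 | 7.8 |
| 5% | all | none | 5.0 | 4.8 | 4.5 | 4.3 | 18.5 |
| 5% | half | none | 5.0 | 7.3 | 8.1 | 8.4 | 18.5 |
| 5% | either | all | 5.0 | 5.0 | 5.0 | 5.0 | 18.5 |

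Of 120 subjects, 7.8% is about 9 and 18.5% about 22. In the rows without withdrawal the visit columns still fall well short of the proportion ever affected, so the main gap does not depend on dropout.

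**Step 3: the denominator.** If every affected subject withdrew and observed n were the base, the V6 denominator would be 120 × 0.98^3 = 112.9 or 120 × 0.95^3 = 102.9. At h = 5%, about 120 − 102.9 = 17 subjects with an earlier reaction would then be absent from the V6 column. Changing the base alone does not bring them back: 102.9 × 0.05 = 5.1 subjects affected at V6, which is 5.0% of 102.9 or 4.3% of 120. Only a subject-level variable counts them.

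**Step 4: do the AE tables supply the missing figure?** They count subjects, but only for findings recorded as AEs. They are laid out by system organ class and preferred term, with no specified row for any application-site skin reaction. The text available does not say that every finding scored at a skin assessment is also entered as an AE.

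**The case against.** The AE tables are the best defence. For a reaction recorded as an AE they give its nature (preferred term), a subject-level incidence and a severity, and withdrawals due to it have their own table. Schedule footnote 10 says that events after screening are recorded as AEs, and a new reaction at the application site would ordinarily be one. A reader might infer that the plan yields no incidence of skin reactions at all; these tables show that it does not go that far. What remains is that the footnote does not mention scored skin findings, so mild ones may never reach the AE tables, and no pooled application-site row is planned.

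A reader might also infer that subjects who leave because of a reaction are dropped from later percentages, so that the V6 figure flatters the more irritating arm. The documents do not say this. The percentage base is not stated, and n and the number missing are shown. SAP 4.2.2.2 refers to a Visit 6/EOT date, which may mean that some early leavers are assessed at the end of treatment. Even on observed n the direction is not fixed. At h = 5%, complete withdrawal of affected subjects moves the V6 figure from 8.4% to 5.0% if half of reactions resolve between visits, but from 4.3% to 5.0% if all do.

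Three smaller points stand. Exclusion criterion 16 bars current irritation or redness at the planned site, so baseline findings should be few. SAP 4.1.1 promises listings by subject and time point, so the figures could be counted by hand; what is absent is a pre-specified table. Safety is otherwise descriptive, so confidence intervals for arm differences are a matter of choice.

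The grading scale and Protocol 8.3.3, which the synopsis cites for safety endpoints, are not in the text available. No criticism of either is made here.

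**Conclusion.** The point holds in a limited form. The scheduled skin assessment is summarised only by visit, and that summary does not measure the incidence named in SAP 1.1.2 or give a worst grade per subject. The AE tables cover part of the endpoint, to an extent that the documents leave open.

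The size is illustrative only: 5% at each of four visits fits 5% to 20% ever affected, and in the simple course above the visit columns show 1.9% to 3.6% against 7.8% ever affected, or 4.3% to 8.4% against 18.5%. These rest on assumed rates, resolution and withdrawal.

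Loss of withdrawn subjects from later denominators is a risk to close by stating the base, not a demonstrated bias. This is a reporting gap in a safety endpoint; the primary analysis and the power are unaffected.

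**What to change.** In SAP 4.3.2.3 add one table for the safety set, by actual treatment, with:

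- the number and percentage of subjects with any skin finding that is new or worse than at the V2 pre-application assessment, at any post-baseline assessment;
- the worst post-baseline grade per subject;
- all treated subjects as the denominator, with the number who have no post-baseline assessment shown, since they would otherwise count silently as unaffected.

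Define worsening on the scale in use, and state whether scored skin findings are also recorded as AEs. Keep the by-visit table as supportive and name its percentage base. AMZ001-minus-placebo differences with 95% confidence intervals may be added but are optional.

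The cost is one derived variable and one table from data already collected, with a change to SAP wording only.

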# 5 Quality control

Programs used to derive the subject-level ADaM analysis dataset and the efficacy endpoints from the SDTM domains will be reviewed through parallel programming by an independent programmer. Other ADaM datasets will be reviewed by code review. Furthermore, the programs involving the statistical analyses of primary and secondary efficacy endpoints will be reviewed using parallel programming by an independent statistician. For the review of outputs, it is not necessary that the formats or layouts match.

Other output programs will be reviewed by the method of code review. All quality control activities for individual programs will be carried out in compliance with SOP 703, Programming of Single Use SAS Programs. All review findings and their follow-up will be documented in a Program Overview Form.

# 6 Layout of output

An ICH E3 based numbering will apply for the EOT documents. RTF files in landscape orientation will be used as the format for single output files with font type as Times New Roman of size 9. PNG files will be used for graphics, and Microsoft Office Word 2010 (or later) files (DOCX) files will be used as the format for TLF collections (EOT documents).

All output will be produced using SAS version 9.4 or a later version.

The sponsor name, protocol number, SAS program and output name and run date will appear bottom right in a footnote. The header of the EOT document will include date of collection and status (draft/final).

On an agreed timeline before the Database Release Meeting, a draft version of the EOT documents using dummy treatment groups will be produced and distributed for review. An Output Review Meeting will be held to consolidate the review findings and prepare a list of revision requests to be used for the second draft of the EOT documents. The second delivery of EOT documents (with dummy treatment groups) will have been subject to full QC.

